4.6 Rater Qualifications

Raters must demonstrate sufficient assessment experience as well as appropriate educational background and indication experience.

Raters performing the clinical assessments will require training and approval by the Sponsor designated vendor prior to rating in this study.

The vendors designated by the Sponsor will conduct rater qualification and will provide documentation about each rater's certification and/or training.

If possible, each subject will be interviewed and assessed throughout the study by the same rater.

5 STUDY DRUG INFORMATION

5.1 Study Drug Administration

The study drug will be administered as a single oral dose. Patients will receive one of the following:

Day 1 Dosing

- Arm 1: 75 mg REL-1017 powder prepared as a solution with Ocean Spray® Diet Cranberry Juice on site to obtain a final volume of 100 mL for dosing
- Arm 2: 100 mg REL-1017 powder prepared as a solution with Ocean Spray® Diet Cranberry Juice on site to obtain a final volume of 100 mL for dosing
- Arm 3: 100 mL of Ocean Spray® Diet Cranberry juice (Placebo).

Day 2-6 Dosing

- Arm 1: 25 mg REL-1017 powder prepared as a solution with Ocean Spray® Diet Cranberry Juice on site to obtain a final volume of 100 mL for dosing;
- Arm 2: 50 mg REL-1017 powder prepared as a solution with Ocean Spray® Diet Cranberry Juice on site to obtain a final volume of 100 mL for dosing; or,
- Arm 3: 100 mL of Ocean Spray® Diet Cranberry juice (Placebo).

The administration of study drug must be observed by a staff member. After drinking the 100 mL of study drug, 25 mL of non-carbonated water will be added to the study drug container and gently swirled. The patient will drink this rinse volume followed by 125 mL of non-carbonated water to drink immediately thereafter. All dosing must be completed within 5 minutes.

Dosing will take place once daily in the morning after an overnight fast (at least 8 hours).

5.2 Study Drug Identification

The investigational product, REL-1017, is composed of d-methadone HCl as a powder and prepared as a solution with Ocean Spray® Diet Cranberry Juice on site to obtain a final volume of 100 mL for dosing. The drug product will be supplied by the Sponsor. The study drug will be administered as a solution of 25 mg, 50 mg, 75 mg or 100 mg REL-1017, based on randomization prepared in Ocean Spray® Diet Cranberry Juice with a final volume of 100 mL

Patients will continue to take the same, stabilized antidepressant medication that they were taking at Screening throughout the course of the study, and the supply of medication during the confined study period will be arranged and assured by the Investigator.

An unblinded pharmacist will assign study drug to patients according to randomized treatment codes provided by the Interactive Web Response System (IWRS). The randomization code used in the IWRS will be prepared by a statistician who is not working as a statistician on the study in any other capacity. The study drug solution will be prepared within 3 hours of administration in

blinded containers, and then will be dispensed to blinded study staff for administration to the patients.

After drinking the 100 mL of study drug, 25 mL of non-carbonated water will be added to the study drug container and gently swirled. The patient will drink this rinse volume followed by 125mL of non-carbonated water to drink immediately thereafter.

All dosing must be completed within 5 minutes.

Dosing will take place once daily in the morning after an overnight fast of at least 8 hours.

5.2.1 Packaging and Labeling

Each container of study drug will be clearly labeled with study-specific information meeting all the applicable regulatory requirements.

Clinical study drug supply labels will bear the following information:

- Statement indicating that the drug is an investigational drug.
- Name, number, or identifying mark of the drug.
- Re-test date of the drug.
- Recommended storage conditions of the drug.
- Lot number of the drug.
- Name and address of the Sponsor.
- Protocol code or study ID.
- Quantity of drug per container.

The pharmacy staff at each site will record the following information for the Ocean Spray® Diet Cranberry Juice that is used for Placebo and to dissolve the REL-1017 for administration during the clinical study:

- Type of container, e.g., plastic bottle, aluminum can.
- Size of container.
- Name and address of the manufacturer/distributor.
- Lot number.
- Expiration/use buy/sell by/best if used by date.

5.2.2 Handling, Storage, and Accountability

All study drug will be transported, received, stored, and handled strictly in accordance with the container or product label, the instructions supplied to the research site and its designated pharmacy, the site's standard operating procedures (SOPs), and applicable regulations (*Guidelines for Temperature Control of Drug Products during Storage and Transportation, GUIDE-0069*). Appropriate storage temperature and transportation conditions will be maintained

for the study drug from the point of manufacture up to delivery of the study drug.

Upon receipt by the study site, the bulk study drugs will be promptly transferred to the appropriate environmentally controlled storage area. The research pharmacy staff will examine the shipment and temperature monitoring devices (if applicable) to verify that the bulk study drugs were received in acceptable condition. Once inspected, the bulk study drugs will be stored in a restricted access, secured area with access limited to authorized research site staff, under physical conditions consistent with the investigational product's specific requirements. After study drug is dispensed to patients, the remaining bulk study drug will be returned to storage in a restricted access, secured area under physical conditions consistent with the investigational product's specific requirements.

The research site's pharmacist or delegate is responsible for ensuring that all bulk study drug received at the site is inventoried and accounted for throughout the study, according to applicable regulations. All containers of dispensed study drug that have been provided to the patients will be returned to the pharmacy, and any volume of unused study drug will be recorded. Dispensed study drugs that have not been used will not be provided to patients again (even to the same patient), nor relabeled or reassigned for use by other patients. Study drugs that have been dispensed, but not used, will be stored and disposed of according to the Sponsor's instructions.

The contents of dispensed study drug containers will not be combined. Unused bulk study drugs and dispensed study drugs will be available for verification by the Sponsor's site monitor.

5.2.3 Dispensing

The study drug will be dissolved in Ocean Spray® Diet Cranberry Juice. Details regarding the preparation and administration of the study drug will be outlined in the pharmacy manual. The study drug solution will be prepared within 3 hours of administration. Only eligible patients participating in the study will receive the study drug. Only authorized research site staff may supply or administer the study drug.

5.3 Method of Assigning Patients to Treatment Groups

Randomization will be used to avoid bias in the assignment of patients to treatment, to increase the likelihood that known and unknown patient attributes (e.g., demographics and Baseline characteristics) are evenly balanced between treatment groups, and to enhance the validity of statistical comparisons between treatment groups.

Each potential patient will be assigned a unique number in the Screening process (Patient ID Number). This number will be used to identify the patient throughout the study. Patients who are randomized will be assigned a unique randomization number. Once any patient number is assigned, it cannot be reassigned to any other patient.

All randomization codes will be generated by the designated unblinded statistician at Syneos Health, Inc., (formerly INC Research, Inc.) before the start of the study. The treatment assignment for each subject will be assigned through the IWRS in a 1:1:1 ratio (REL-1017 25 mg, REL-1017 50 mg, or Placebo). Stratified randomization will be used to achieve a reasonable balance of patients taking cytochrome (CYP) 2B6 inhibitor ADTs versus patients who

take non-CYP2B6 inhibitors within the three treatment groups. A randomization list will be computer-generated for each of the two strata using random permuted blocks (first strata: patients receiving concomitant ADTs that are cytochrome CYP2B6 inhibitors: paroxetine, fluoxetine, sertraline; second strata: patients receiving concomitant ADTs that are not CYP2B6 inhibitors). The goal of stratified randomization is to end the study with a similar number of patients taking CYP2B6 inhibitors in each study treatment group (e.g., if 15 patients are randomized who are taking ADTs with CYP2B6 inhibitor activity, then approximately 5 will be in the REL-1017 25 mg group, 5 will be in the REL-1017 50 mg group, and 5 will be in the Placebo group). Stratification will allow for subgroup exploratory analyses to be interpreted more easily after the study is complete and unblinded.

If applicable, replacement patients for patients who withdraw prior to dosing will receive the same treatment allocation as those whom they replace.

5.4 Selection of Doses

Since extensive clinical experience is available for racemic methadone and some clinical experience for d-methadone,^{31,32,33} the 25 mg and 50 mg doses are selected based on the comparative characteristics of racemic methadone and available data with d-methadone in healthy patients.

The following rationale was applied. In recent studies in healthy patients, an oral dose of at least 0.2 g/kg (10 mg to 20 mg) or 8 mg to 15 mg was well tolerated and provided information on the PK of individual isomers and the interaction with other CYP3A4 substrate drugs.³⁴ Moreover, in the study of REL-1017 alone in opiate-naive patients, a dose as high as 150 mg was tested with no severe adverse reactions. Due to differences in the pharmacologic activity of the methadone enantiomers, the same incidence and severity of opioid-related AEs observed with racemic methadone are not anticipated to occur with the administration of d-methadone.

Based on the safety data from Protocol REL-1017-111, single doses of 5 mg, 20 mg, 60 mg, 100 mg, and 150 mg of REL-1017 or Placebo were well tolerated. The results of Protocol REL-1017-112 evaluated 10 days of dosing with as high as 75 mg, and no impact on safety was observed. Regardless of the confirmed dose proportionality, the comparison of concentration and exposure between the 50 mg and 75 mg REL-1017 treatment groups demonstrated only slight differences. Consequently, 25 mg and 50 mg doses were chosen for administration in Protocol REL-1017-202 as daily doses over a period of 7 days.

To reach steady state more quickly for REL-1017 25 mg and REL-1017 75 mg dosing arms, a loading dose on Day 1 was added to each dosing arm, REL-1017 75 mg on Day 1 followed by 25 mg REL-1017 on Day 2-7; 100 mg REL-1017 on Day 1 followed by 50 mg REL-1017 on Day 2-7.

PK/PD modelling, based on the demonstrated AUC_{τ} of d-methadone in pre-clinical and clinical studies and on the AUC_{τ} of ketamine at doses that provide antidepressant efficacy, supports the conclusion that d-methadone 25 mg and 50 mg QD are the predicted efficacious doses.

5.5 Blinding and Unblinding Procedures

The REL-1017 powder will be dissolved in a strong-tasting juice/drink (Ocean Spray[®] Diet Cranberry Juice) to mask the taste of the d-methadone. This will help to maintain the blind. Also, patients who are randomized to receive Placebo will receive an equivalent volume of Ocean Spray[®] Diet Cranberry Juice.

5.6 Treatment Phase

The only persons with access to the blinding schema during the treatment phase will be the designated pharmacy personnel who are responsible for the dispensing of study drug, the compliance auditor(s) who verify conformity to study procedures, and the unblinded statisticians who generate the code. Under normal circumstances, the blind will not be broken until all patients have completed treatment. Blinded dosing information will be broken only in an emergency where knowledge of the dosing information could impact further treatment decisions or aid in the emergency treatment of a patient. Individual code breaks will result in the withdrawal of the patient from the study. The date, time, and reason for the unblinding will be documented in the appropriate section of the eCRF and in the source documents.

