4.5 Patient Discontinuation/Withdrawal Criteria

Any patient who voluntarily withdraws consent or is discontinued (e.g., because of an AE) from the study prior to completion will be considered as withdrawn from the study. Patients may be discontinued from the study for any reason including any of the following circumstances:

- Occurrence of intolerable AE, as assessed by the Investigator or designee.
- Clinically significant abnormality on vital signs, electrocardiogram (ECG), clinical

laboratory, or physical examination evaluations, as assessed by the Investigator or designee.

- Subjects with a QTcF ≥ 500 msec or ≥ 60 msec above the patient's Baseline value will discontinue study medication and be re-assessed. The ECG should be repeated until values return below 500 msec, or ≥ 60 msec above Baseline. These findings will be reviewed by a cardiologist. Any additional intervention for the safety of the subject should be discussed with the Study Medical Monitor and Sponsor.
- ALT or AST ≥ 2 x ULN.
- Withdrawal of consent.
- Lost to follow-up.
- Administrative reasons (e.g., Sponsor decision).
- Major violation of the protocol.
- If in the opinion of the qualified Investigator, it is in the best interest of the patient.
- Non-compliance with study requirements and restrictions.
- Use of a concomitant medication that, in the opinion of the Investigator or designee, could interfere with the study procedures or data integrity or compromise the safety of the patient.
- Positive breath alcohol test at Check-in to the CRU.
- Termination of the study.

When an event such as a family emergency, a transient intercurrent illness (e.g., a cold) unrelated to study drug, or a remediable act of non-compliance prevents a patient from Check-in to the CRU, but the patient wishes to continue in the study, with the agreement of the Investigator, the research site staff may attempt to reschedule the Check-in and retain the patient in the study.

If a patient is prematurely discontinued from participation in the study for any reason after study drug administration, the Investigator or designee must make every effort to perform the assessments scheduled for the Day 14 visit (7 days after the last dose of study drug). The reason for withdrawal will be recorded in the eCRF and the patient's source medical record.

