In the event of a patient discontinuation following dosing, PK and safety assessments may continue at the discretion of the Investigator based on the time points outlined in the Time and Events Schedule ([Table 1](#)).

Patients who are randomized, but not dosed, may be replaced. Patients who receive at least one dose of study drug, but are withdrawn prior to study completion, will not be replaced.

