7.4 Follow-Up of Adverse Events and Serious Adverse Events

All unresolved AEs will be followed for up to a minimum of *14 days* after the patient's final dose of study drug on Day 7 unless the Investigator's judgment dictates otherwise, the event has resolved or stabilized before Day 21, or the patient is lost to follow-up.

All AEs that result in discontinuation and all SAEs will be followed until one of the following occurs:

- The event resolves.

- The event stabilizes.
- The event returns to a Baseline value, if a Baseline value is available.
- The event can be attributed to agent(s) other than the study drug or to factors unrelated to study conduct.

When it becomes unlikely that any additional information can be obtained (e.g., patient or health care practitioner refuses to provide additional information, the patient is lost to follow-up), the Investigator or designee will ensure that the follow-up includes any pertinent supplemental investigations (e.g., laboratory tests or investigations, histopathological examinations, or consultation with other health care professionals) to elucidate the nature and/or causality of the AE or SAE.

Investigators are not obligated to actively seek AEs or SAEs in former study patients that occur after the Follow-Up Period. However, if the Investigator or designee learns of any AE or SAE at any time after a patient has been discharged from the study and the event is considered as reasonably related to the study drug, the Investigator will notify Relmada.

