8.1.4.2 Adverse Events

Original terms used in the eCRFs by Investigators or designees to identify AEs will be coded using the MedDRA (Version 16.0 or higher). The number and percentage of patients with treatment-emergent AEs will be summarized by system-organ-class, preferred term, and treatment and for each treatment by maximum severity and relationship to study treatment. A treatment-emergent AE is any that is new in onset or was aggravated in severity or frequency following the first dose of study drug (Day 1), up to and including the last visit of the study (Day 21).

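### An emergency code break withdraws the patient from the study, leaving later scheduled safety assessments discretionary or unclear

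*Combined protocol and SAP*

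**What the plan says.** Section 5.6 sets the condition for unblinding: "Blinded dosing information will be broken only in an emergency where knowledge of the dosing information could impact further treatment decisions". It then sets the consequence: "Individual code breaks will result in the withdrawal of the patient from the study". The date, time and reason for unblinding are recorded. The section does not separate leaving the study from stopping study drug, and it does not refer to the follow-up rules elsewhere.

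Section 4.5 defines withdrawal broadly. A patient who "is discontinued (e.g., because of an AE) from the study prior to completion will be considered as withdrawn from the study". After such a discontinuation the investigator "must make every effort to perform the assessments scheduled for the Day 14 visit". Beyond that visit, "PK and safety assessments may continue at the discretion of the Investigator based on the time points outlined" in Table 1.

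Section 7.4 adds: "All AEs that result in discontinuation and all SAEs will be followed until one of the following occurs", the end points being that the event settles or is explained by another cause.

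Sections 6.1.4, 6.1.6 and 6.1.8 cover the end-of-dosing assessments, the inpatient stay and the follow-up interview. Each expressly covers patients who stop study drug early. None mentions a patient withdrawn from the study.

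On analysis, Section 8.1.1 keeps every randomized and treated patient in the Safety population. Section 8.1.4.2 summarizes treatment-emergent adverse events as numbers and percentages of patients, over a window running "up to and including the last visit of the study (Day 21").

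**The concern.** Safety and tolerability is the primary objective. A code break is triggered by a safety emergency, so the rule in Section 5.6 selects patients on something closely tied to that endpoint and moves them to the weaker of two follow-up regimes. A code break is not a withdrawal of consent, so nothing on the patient's side requires this.

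The primary endpoint in Section 8.1.3.1 is wider than adverse events. It includes ECG, laboratory tests, C-SSRS, CADSS, COWS and the 4-Item PSRS, and these exist only if the scheduled assessment takes place. If scheduled contacts are missed while the patient stays in the denominator, a later event that nobody saw is counted as no event. If emergencies are more common in one arm, observation is shorter in that arm. Efficacy ratings may also be missed, and Section 8.1.7 would handle them as missing at random although the reason for missingness was an emergency.

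**Working it through.** The plan gives no figure that depends on this rule, so the check sets the provisions side by side and then counts the assessments exposed.

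**1. What each kind of patient is promised after dosing**

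| Item | Stops study drug only | Withdrawn from the study |
|---|---|---|
| End-of-dosing assessments | Kept while consent stands (6.1.4) | Not stated; PK and safety discretionary (4.5) |
| At least 2 further inpatient days | Kept (6.1.6) | Unclear: worded for each patient, but names only those stopping drug |
| Day 14 assessments | Kept, 7 days after last dose (6.1.7) | Best effort (4.5) |
| Follow-up interview | Kept, 14 days after last dose (6.1.8) | Unclear: worded for all patients, but names only those stopping drug |
| Known SAEs and AEs leading to discontinuation | Followed (7.4) | Followed (7.4) |

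The two columns agree in the last row. In the others the right-hand column is weaker or undetermined.

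**2. Which scheduled safety measurements depend on the unclear rows** (Table 1 and Section 6.2.6)

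| Measure | Scheduled days | Backed by the Day 14 best effort | Exposed |
|---|---|---|---|
| C-SSRS after Day 2 | 8, 9, 14, 21 | 1 of 4 | 8, 9, 21 |
| COWS | 8, 9, 14 | 1 of 3 | 8, 9 |
| CADSS and 4-Item PSRS after Day 1 | 7, 9 | 0 of 2 | 7, 9 |

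These are the most that could be missed; a later code break exposes fewer. Depending on timing, the Day 7 laboratory tests and the daily ECGs up to Day 9 are exposed in the same way.

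**3. Observation time.** If the Day 14 visit is the last contact, observation after the last dose is 7 days instead of 14, or 7/14 = 50% of the planned period.

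**4. Size.** The documents give no code-break rate. With about 20 patients per arm, one patient is 1/20 = 5% of an arm, and one unobserved event would lower that arm's adverse event percentage by 5 percentage points. As an assumption only, 0 to 2 code breaks in the trial would affect from 0/20 = 0% to 2/20 = 10% of a single arm, the upper end if both fell in the same arm.

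**The case against.** A reader might infer that the rule loses safety follow-up in the very patients with the most serious events. The documents do not support that. An event grave enough to break the blind would usually be an SAE or lead to discontinuation, and Section 7.4 follows those with no fixed end date, possibly beyond Day 21. The event has also happened before the withdrawal, so it is counted in the Safety population. Section 4.5 does not stop at Day 14: it permits the other scheduled PK and safety assessments. Sections 6.1.6 and 6.1.8 speak of each patient and of all patients, and Section 7 has all adverse events recorded to the end of the Follow-Up Period. The safety analysis is descriptive, so no planned between-arm test could be biased. The date of unblinding is already captured.

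All of this stands, and it limits the point. It does not remove it. Section 7.4 follows events already known; it schedules neither rating scales nor a search for new events. Permission at the investigator's discretion is not a requirement. The broad wording of Sections 6.1.6 and 6.1.8 can be set against Section 4.5, which would not need a discretionary rule if the full schedule already bound withdrawn patients. Section 5.6 does not say which reading applies.

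**Conclusion.** The point holds as an unresolved and partly discretionary schedule after a code break. It does not hold as a loss of safety follow-up. What may be incomplete is the scheduled C-SSRS, COWS, CADSS, 4-Item PSRS, ECG and laboratory data, and the detection of new adverse events to Day 21, in a few patients selected by an emergency.

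The expected size is small because code breaks should be rare, and with none there is no effect. That rarity is an assumption, as is any difference in emergencies between arms; the documents support no figure for either. The point is still worth settling because in arms of about 20, with a descriptive primary safety endpoint, one incompletely observed serious case is visible in the tables.

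**What to change.** Reconcile Section 5.6 with Sections 4.5, 6.1 and 7.4. State in Section 5.6 that a code break does not by itself end the scheduled safety and follow-up assessments through Day 21, that these continue unless consent is withdrawn, and that the follow-up rules in the other three sections apply. This is the consent-based standard that Section 6.1.4 already uses for patients who stop study drug. In the analysis, flag ratings made after the recorded date and time of unblinding.

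What a code break means for study drug dosing should be left to the sponsor's clinical text; this change sets no rule on it.

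The cost is a sentence or two in the protocol and a flag in the data. No assessment is added to Table 1. The downside is that a few ratings will be made with the treatment known, which is why they need the flag.
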